#### 4.1 Pharmaceutical and Therapeutic Background

Refer to the Investigator's Brochure (IB)/approved labeling for detailed background information on Pembrolizumab (MK-3475).

The importance of intact immune surveillance in controlling outgrowth of neoplastic transformation has been known for decades. Accumulating evidence shows a correlation between tumor-infiltrating lymphocytes (TILs) in cancer tissue and favorable prognosis in various malignancies. In particular, the presence of CD8+ T-cells and the ratio of CD8+ effector T-cells / FoxP3+ regulatory T-cells seems to correlate with improved prognosis and long-term survival in many solid tumors.

The PD-1 receptor-ligand interaction is a major pathway hijacked by tumors to suppress immune control. The normal function of PD-1, expressed on the cell surface of activated T-cells under healthy conditions, is to down-modulate unwanted or excessive immune responses, including autoimmune reactions. PD-1 (encoded by the gene *Pdcd1*) is an Ig superfamily member related to CD28 and CTLA-4 which has been shown to negatively regulate antigen receptor signaling upon engagement of its ligands (PD-L1 and/or PD-L2). The structure of murine PD-1 has been resolved. PD-1 and family members are type I transmembrane glycoproteins containing an Ig Variable-type (V-type) domain responsible for ligand binding and a cytoplasmic tail which is responsible for the binding of signaling molecules. The cytoplasmic tail of PD-1 contains 2 tyrosine-based signaling motifs, an immunoreceptor tyrosine-based inhibition motif (ITIM) and an immunoreceptor tyrosine-based switch motif (ITSM). Following T-cell stimulation, PD-1 recruits the tyrosine phosphatases SHP-1 and SHP-2 to the ITSM motif within its cytoplasmic tail, leading to the dephosphorylation of effector molecules such as CD3 $\zeta$ , PKC $\theta$  and ZAP70 which are involved in the CD3 T-cell signaling cascade. The mechanism by which PD-1 down modulates T-cell responses is similar to, but distinct from that of CTLA-4 as both molecules regulate an overlapping set of signaling proteins. PD-1 was shown to be expressed on activated lymphocytes including peripheral CD4+ and CD8+ T-cells, B-cells, Tregs and Natural Killer cells. Expression has also been shown during thymic development on CD4-CD8- (double negative) T-cells as well as subsets of macrophages and

dendritic cells. The ligands for PD-1 (PD-L1 and PD-L2) are constitutively expressed or can be induced in a variety of cell types, including non-hematopoietic tissues as well as in various tumors. Both ligands are type I transmembrane receptors containing both IgV- and IgC-like domains in the extracellular region and contain short cytoplasmic regions with no known signaling motifs. Binding of either PD-1 ligand to PD-1 inhibits T-cell activation triggered through the T-cell receptor. PD-L1 is expressed at low levels on various non-hematopoietic tissues, most notably on vascular endothelium, whereas PD-L2 protein is only detectably expressed on antigen-presenting cells found in lymphoid tissue or chronic inflammatory environments. PD-L2 is thought to control immune T-cell activation in lymphoid organs, whereas PD-L1 serves to dampen unwarranted T-cell function in peripheral tissues. Although healthy organs express little (if any) PD-L1, a variety of cancers were demonstrated to express abundant levels of this T-cell inhibitor. PD-1 has been suggested to regulate tumor-specific T-cell expansion in subjects with melanoma (MEL). This suggests that the PD-1/PD-L1 pathway plays a critical role in tumor immune evasion and should be considered as an attractive target for therapeutic intervention.

Pembrolizumab is a potent and highly selective humanized monoclonal antibody (mAb) of the IgG4/kappa isotype designed to directly block the interaction between PD-1 and its ligands, PD-L1 and PD-L2. Keytruda™ (pembrolizumab) has recently been approved in the United States for the treatment of patients with unresectable or metastatic melanoma and disease progression following ipilimumab and, if BRAF V600 mutation positive, a BRAF inhibitor. Keytruda is also approved for patients with metastatic NSCLC whose tumors express PD-L1 as determined by an FDA-approved test and who have disease progression on or after platinum-containing chemotherapy.

## **4.2 Rationale**

### **4.2.1 Rationale for Dose Selection/Regimen/Modification**

An open-label Phase I trial (Protocol 001) was conducted to evaluate the safety and clinical activity of single agent MK-3475 (Keytruda™, pembrolizumab). The dose escalation portion of this trial evaluated three dose levels, 1 mg/kg, 3 mg/kg, and 10 mg/kg, administered every 2 weeks (Q2W) in subjects with advanced solid tumors. All three dose levels were well tolerated and no dose-limiting toxicities were observed. This first in human study of MK-3475 showed evidence of target engagement and objective evidence of tumor size reduction at all dose levels (1 mg/kg, 3 mg/kg and 10 mg/kg Q2W). No MTD has been identified to date. Recent data from other clinical studies within the MK-3475 program has shown that a lower dose of MK-3475 and a less frequent schedule may be sufficient for target engagement and clinical activity.

PK data analysis of MK-3475 administered Q2W and Q3W showed slow systemic clearance, limited volume of distribution, and a long half-life (refer to IB). Pharmacodynamic data (IL-2 release assay) suggested that peripheral target engagement is durable (>21 days). This early PK and pharmacodynamic data provides scientific rationale for testing a Q3W dosing schedule in this study.

A population pharmacokinetic analysis has been performed using serum concentration time data from 476 patients. Within the resulting population PK model, clearance and volume parameters of MK-3475 were found to be dependent on body weight. The relationship between clearance and body weight, with an allometric exponent of 0.59, is within the range observed for other antibodies and would support both body weight normalized dosing or a fixed dose across all body weights. MK-3475 has been found to have a wide therapeutic range based on the melanoma indication. The differences in exposure for a 200 mg fixed dose regimen relative to a 2 mg/kg Q3W body weight based regimen are anticipated to remain well within the established exposure margins of 0.5 – 5.0 for MK-3475 in the melanoma indication. The exposure margins are based on the notion of similar efficacy and safety in melanoma at 10 mg/kg Q3W vs. the proposed dose regimen of 2 mg/kg Q3W (i.e. 5-fold higher dose and exposure). The population

PK evaluation revealed that there was no significant impact of tumor burden on exposure. In addition, exposure was similar between the NSCLC and melanoma indications. Therefore, there are no anticipated changes in exposure between different indication settings.

The rationale for further exploration of 2 mg/kg and comparable doses of pembrolizumab in solid tumors was based on: 1) similar efficacy and safety of pembrolizumab when dosed at either 2 mg/kg or 10 mg/kg Q3W in melanoma patients, 2) the flat exposure-response relationships of pembrolizumab for both efficacy and safety in the dose ranges of 2 mg/kg Q3W to 10 mg/kg Q3W, 3) the lack of effect of tumor burden or indication on distribution behavior of pembrolizumab (as assessed by the population PK model) and 4) the assumption that the dynamics of pembrolizumab target engagement will not vary meaningfully with tumor type.

The current study will employ pembrolizumab at a fixed dosage of 200mg every 3 weeks, which is the FDA approved standard dosing. A fixed dose regimen will simplify the dosing regimen to be more convenient for physicians and to reduce potential for dosing errors. A fixed dosing scheme will also reduce complexity in the logistical chain at treatment facilities and reduce wastage.

#### **4.2.2 Rationale for Endpoints**

##### **4.2.2.1 Efficacy Endpoints**

This feasibility study addresses a cohort of patients with established resistance to chemotherapy and HCT by virtue of having relapsed after HCT. We are seeking to identify a signal for clinical benefit by assessing the ORR to pembrolizumab  $\pm$  chemotherapy while providing additional insights into the mechanisms of check-point inhibition in the immune biology of post-HCT relapse. These efficacy endpoints will be assessed by serial CBC, bone marrow biopsies / aspirate, assessing peripheral blast percentages, absolute blast counts (ABC), and marrow blasts.

The time to response in this disease cohort is unknown. The first marrow assessment of disease response will be at day 35 after initiation of study treatment. If disease is stable (SD) or improved (CR or PR) at day 35, clinicians will continue single agent therapy every 3 weeks for a total of 4 doses. A second marrow assessment will be performed on day 77. If CR or PR is attained subjects may proceed to phase II (maintenance) (see section 5.2).

If there is a concern for rapid disease progression or clinical instability, chemotherapy may be added per investigators discretion after the day 35 marrow results (two doses of pembrolizumab) (See section 5.2.1.2).. Subjects may continue study drug in the absence of toxicity attributable to pembrolizumab per Table 3.

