**Table 2 Trial Treatment**

Drug	Dose/Potency	Dose Frequency	Route of Administration	Regimen/Treatment Period	Use
Pembrolizumab (Phase I: Induction)	200 mg	Every 3 weeks	IV infusion	Day 1 of each 3 week cycle x 4 doses	Experimental
Pembrolizumab (Phase II: Maintenance)	200 mg	Every 3 weeks	IV infusion	Day 1 of each 3 week cycle up to 13 doses	Experimental

**Description of Trial Treatment:** Eligible subjects will be initiated on pembrolizumab (phase I) for up to 4 doses with response assessments at day 35 (after 2 doses) and day 77 (after 4 doses). Subjects who are tolerating therapy without drug related adverse events (Table 3) AND who have disease in PR or CR on day 77 response assessment may be continued on pembrolizumab maintenance (phase II). Phase II treatment will continue for up to an additional 13 doses or until either toxicity or progression of malignancy at which time the subject will be placed into follow-up.

**Subjects initiated on systemic induction chemotherapy:** due to progression will receive no additional or concomitant phase I (induction) doses of pembrolizumab but may be considered for phase II maintenance pembrolizumab if disease assessment at day 77 (following chemotherapy) indicates PR or CR. Pembrolizumab may have synergistic effects with chemotherapy and/or facilitate augmentation of GVL after reduction of high leukemic burden.

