#### **5.8 Clinical Criteria for Early Trial Termination**

As a feasibility trial in which patients may receive the standard of care in addition to pembrolizumab therapy at the discretion of the treating physician, stopping rules for FUTILITY are not indicated.

Stopping rules for TOXICITY are outlined in section 8

Early trial termination will be the result of the criteria specified below:

1. Quality or quantity of data recording is inaccurate or incomplete

2. Poor adherence to protocol and regulatory requirements
3. Incidence or severity of adverse drug reaction in this or other studies indicates a potential health hazard to subjects
4. Plans to modify or discontinue the development of the study drug

In the event of Merck decision to no longer supply study drug, ample notification will be provided so that appropriate adjustments to subject treatment can be made.

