¶ PK and anti-pembrolizumab Ab testing may be performed as a component of the research lab testing, as indicated. These studies will be performed after collaboration with the sponsor (Merck)

\*\* Chimerism studies (lineage specific) when sent as part of routine care will be recorded as percentage of donor cells (CD3 and CD33).

Note: Every effort will be made to collect bone marrow and blood samples for efficacy and correlative specimens for research purposes. Efficacy and correlative studies not obtained during the treatment and post-treatment for clinical reasons (e.g. intercurrent illness, leukemia progression receiving concomitant chemotherapy, myeloid sarcoma) will not constitute a protocol deviation.

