## **8.0 STATISTICAL ANALYSIS PLAN**

### **8.1 Statistical Analysis Plan Summary**

The statistical plan for this feasibility study of pembrolizumab for relapse after HCT is primarily directed toward the primary objective of safety and feasibility after HCT. The trial will additionally estimate the proportion of patients responding to pembrolizumab monotherapy by overall response rate (ORR). The ORR (CR+PR) will also be estimated at day 35 and 77 for subjects receiving  $\geq$  one dose of single agent pembrolizumab. If progression is noted subjects may receive standard induction chemotherapy. Subjects who are administered standard induction chemotherapy prior to day 77 (for any reason) will be considered non-responders for ORR of pembrolizumab monotherapy. However, we will perform a planned subset analysis to determine the ORR at day 77 for subjects receiving pembrolizumab followed by systemic chemotherapy.

The incidence of grade 3-4 acute GvHD and significant ( $\geq$  grade 3) immune mediated toxicities will be estimated at the conclusion of the treatment period which is 30 days after the last dose of pembrolizumab. Overall survival (OS) and Disease Free Survival (DFS) at 12 months will be calculated by Kaplan Meier methods. The observation period for OS and DFS will begin at the confirmed date of relapse after HCT until death or last scheduled clinical follow up. These observations will assist in determining whether further investigations are warranted after HCT.

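### Sections 4.2.2.1 and 5.2 do not agree on whether pembrolizumab induction doses may continue once chemotherapy starts, leaving exposure, one day-77 response rate and the GvHD stopping window open

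*Combined protocol and SAP*

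**What the plan says.** Section 4.2.2.1 of the combined protocol and SAP states that, where rapid progression or clinical instability is a concern, "chemotherapy may be added per investigators discretion after the day 35 marrow results (two doses of pembrolizumab"). The next sentence reads: "Subjects may continue study drug in the absence of toxicity attributable to pembrolizumab per Table 3". Toxicity is the only limit given.

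The text under Table 2 in section 5.2 takes subjects started on systemic induction chemotherapy because of progression and says they "will receive no additional or concomitant phase I (induction) doses of pembrolizumab but may be considered for phase II maintenance pembrolizumab", the latter if the day-77 assessment shows PR or CR.

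Section 5.2.1.2 lists when chemotherapy may be started and which regimens are allowed. It ends pembrolizumab for subjects given other investigational agents, but does not say whether induction doses stop when permitted chemotherapy begins.

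Section 8.1 plans a subset analysis of the "ORR at day 77 for subjects receiving pembrolizumab followed by systemic chemotherapy". Section 8.2.4 monitors severe acute GvHD for the stopping rule until 30 days after the last induction dose, and the interim looks at 10 and 15 patients use the same anchor.

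**The concern.** The question arises soon after the day-35 marrow, because dose 3 is due on D43. An investigator who has just started chemotherapy can find support in 4.2.2.1 for giving doses 3 and 4, and in 5.2 a bar on giving them.

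Three things depend on the answer: how much induction pembrolizumab a chemotherapy-treated subject receives; whether the day-77 ORR with or without chemotherapy describes two doses followed by chemotherapy, up to four doses overlapping it, or a mixture; and how long such a subject is observed for the severe-GvHD stopping rule. Section 8.2.2 expects some but not all of the 20 subjects to receive chemotherapy, so the situation is an anticipated one. Section 8.2.3 names safety and feasibility as the primary endpoint.

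**Working it through.** **1. Does other text settle it?** The remaining references point both ways.
- Fits concurrent use: 5.8 says "patients may receive the standard of care in addition to pembrolizumab therapy at the discretion of the treating physician", and the closing note to the flow chart in section 6.0 mentions "leukemia progression receiving concomitant chemotherapy". Neither is a dosing instruction; the first explains why there is no futility rule and the second concerns missed samples.
- Fits sequential use: the 8.1 subset, which agrees with 5.2. Section 5.2.1.2 also presents staying on monotherapy as an alternative to chemotherapy.
- Silent: whether induction stops when chemotherapy is started for a reason other than progression. Section 4.2.2.1 includes clinical instability; the bar in 5.2 is worded for progression only.

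**2. The plan's own figures.** The stopping probabilities in 8.2.4 depend on GvHD events counted in the window, so they were checked first. With X ~ Bin(10, p) and Y ~ Bin(5, p):

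P(stop early) = P(X ≥ 6) + Σ over x = 0 to 5 of P(X = x) · P(Y ≥ 9 − x)

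At p = 0.30, 0.40, 0.50 and 0.60 this gives 0.051, 0.186, 0.430 and 0.709, against the stated 0.05, 0.18, 0.43 and 0.71. They reproduce to within one percentage point. The formula takes p as given and does not depend on how long each subject is observed.

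**3. Exposure and window.** Inputs: 200 mg per dose (Table 2); nominal dose days D1, D22, D43 and D64 (section 6.0); window close = day of last induction dose + 30 (8.2.4). The case sized is chemotherapy started after the day-35 marrow.

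| Chemotherapy starts after | Window closes if induction stops | Window closes if all four doses are given | Extra doses | Window difference |
|---|---|---|---|---|
| Dose 2 (D22) | 22 + 30 = D52 | 64 + 30 = D94 | 2 (400 mg) | 42 days |
| Dose 3 (D43) | 43 + 30 = D73 | D94 | 1 (200 mg) | 21 days |
| Dose 4 (D64) | D94 | D94 | 0 | 0 days |

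In the first row, total induction exposure is 2 × 200 = 400 mg or 4 × 200 = 800 mg. D52 falls 77 − 52 = 25 days before the day-77 marrow, and D94 falls 94 − 77 = 17 days after it.

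**4. Which analyses move?**
- Day-77 ORR with or without chemotherapy (4.2.2 and 8.2.1): the treatment it describes depends on the answer.
- Severe acute GvHD for the stopping rule (8.2.4) and for estimation (8.2.1, item a): the window moves as in the table.
- Total GvHD (8.2.1, item b): runs to 90 days after the last infusion. Without maintenance that is 22 + 90 = D112 or 64 + 90 = D154, so observation for this analysis continues well past D52 either way.
- Monotherapy ORR: unchanged, because 8.1 counts any induction chemotherapy before day 77 as non-response.
- Clinical benefit rate: unchanged, because 8.2.2 assesses it before chemotherapy is added.
- Sample size and stopping boundaries: unchanged.

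**The case against.** The strongest reply is that the text can be read consistently. The sentence in 4.2.2.1 is permissive, sits in a rationale section and does not name induction doses. It could be a general tolerability condition, or refer to later maintenance, for which 5.2 uses a similar Table 3 condition. The specific instruction is in 5.2, and a subject managed under it breaches nothing in 4.2.2.1. The Trial Diagram in 2.2, which 5.2 tells the reader to consult, was not visible in the text reviewed and might show the sequence.

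Much of this stands. A reader might infer that the two sections impose instructions that cannot both be obeyed, but a permission and a prohibition do not do that. What remains is that the permission directly follows the sentence on adding chemotherapy and carries no exception, that 5.2.1.2 does not close the question, and that the non-progression case has no clear rule.

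A reader might also infer that the day-77 efficacy results as a whole are compromised. They are not: only the ORR with or without chemotherapy is affected. That endpoint is descriptive and already pools subjects with and without chemotherapy, and regimens chosen by the physician.

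Finally, a reader might infer that the stated stopping probabilities are wrong. Shorter windows could lower the chance of stopping. Suppose a constant hazard, a 60% risk by D94, and 25% to 75% of subjects cut to D52. The risk by D52 is 1 − 0.4^(51/93) = 0.395. The average risk is 0.75 × 0.60 + 0.25 × 0.395 = 0.549 down to 0.25 × 0.60 + 0.75 × 0.395 = 0.446, and the stopping probability falls from 0.71 to between 0.57 and 0.29. The documents give neither the hazard shape nor the share receiving chemotherapy, so this is illustration only and the point does not rest on it.

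**Conclusion.** The point holds as an unresolved inconsistency with limited reach. For a subject who progresses at day 35 and starts chemotherapy, 4.2.2.1 can be read as permitting doses 3 and 4 while 5.2 bars them. For chemotherapy started because of clinical instability, the documents leave a gap rather than a conflict.

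The 42-day difference is a maximum, not a typical value. It needs chemotherapy to start between the day-35 marrow and dose 3, and both remaining doses to be given under the permissive reading. It uses nominal days and ignores visit windows and toxicity holds. Chemotherapy before day 35 is discouraged in 5.2.1.2, is not the case addressed by the sentence in 4.2.2.1, and is left out of this sizing. How many of the 20 subjects would be affected cannot be derived from the documents.

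Because the matter bears on exposure and safety observation and is simple to correct, it should be corrected.

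**What to change.** Reconcile 4.2.2.1, 5.2 and 5.2.1.2 into a single instruction on whether induction pembrolizumab may be given once chemotherapy has started, covering every reason for starting it: progression on the day-35 marrow, impending rapid progression, and clinical instability. Which rule to adopt is for the investigators and sponsor.

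Then bring the statistical text into line:
- Define the day-77 chemotherapy subset in 8.1, and the ORR with or without chemotherapy in 4.2.2 and 8.2.1, by the sequence that the instruction produces.
- State in 8.2.4 when the severe-GvHD window closes for a subject who starts chemotherapy during induction, and apply the same definition at the interim looks.
- Adjust the incidental wording in 5.8 and the closing note to section 6.0 so that it no longer suggests a different rule.

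The cost is amendment or clarification wording. Sample size, boundaries and assessment schedule need not change.

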#### **Primary objective endpoints:**

Efficacy:

- ORR at days 35 and 77 in subjects receiving pembrolizumab monotherapy
- ORR at day 77 in subjects receiving pembrolizumab  $\pm$  standard induction chemotherapy
- Clinical Benefit Rate (CBR) at days 35 and 77 in subjects receiving pembrolizumab monotherapy

Safety:

- Incidence and severity of GvHD after administration of pembrolizumab
- Grade 3-5 Regimen-related toxicities (RRT) per CTCAE v4
- Incidence of immune mediated toxicities attributable to pembrolizumab

**Secondary objective endpoints:**

- Estimate overall survival (OS) and disease-free survival (DFS) at one year in patients who receive pembrolizumab for relapse after allogeneic HCT.

## **5.0 METHODOLOGY**

### **5.1 Entry Criteria**

#### **5.1.1 Diagnosis/Condition for Entry into the Trial**

[Please refer to section 5.1.2.](#)

#### **5.1.2 Subject Inclusion Criteria**

In order to be eligible for participation in this trial, the subject must:

1. Acute Myeloid Leukemia (AML), Acute Lymphoblastic Leukemia (ALL) or Myelodysplastic Syndrome (MDS) in confirmed relapse based on bone marrow examination after allogeneic HCT. Biopsy confirmed myeloid sarcoma or extramedullary AML may also be considered.
2. Confirmation of 'measurable disease' by blast % will be defined as a marrow blast percentage of > 5% by morphologic assessment on bone marrow examination. This criterion does not apply to myeloid sarcoma, or extramedullary leukemia, which must also show measurable lesion by CT, MRI, PET/CT or photograph (i.e. Leukemia cutis). If marrow blasts of ≤ 5% blasts are enumerated the patient may be eligible only if there is clear (probable or definite) flow cytometric, cytogenetic or molecular aberrations (e.g. FLT3-ITD, NPM1, etc.) documenting relapse of the leukemia associated clone defined prior to HCT.
3. Patient may not have received definitive salvage chemotherapy for their post-transplant relapse within the past 21 days. Use of hydroxyurea is permitted.
4. Be willing and able to provide written informed consent/assent for the trial
5. Be ≥ 18 years of age on day of signing informed consent
6. Be willing to provide tissue from bone marrow biopsies
7. Have a performance status of 0, to 1 on the ECOG Performance Scale. For purposes of HCT, this will correspond to a Karnofsky Performance status of ≥ 80%

8. Demonstrate adequate organ function as defined in Table 1, all screening labs should be performed within 10 days of treatment initiation

